The primary outcome for the national study is a composite outcome of neonatal mortality and morbidity likely to be related to the quality of intrapartum care: stillbirth after presentation in labour, early neonatal death (within 7 days of birth), neonatal encephalopathy, meconium aspiration, brachial plexus injury, fractured humerus or clavicle. The incidence of this composite outcome in women judged to be at “low risk” when presenting in labour has been used to determine the sample size needed for the national study to have adequate power to detect clinically important differences in outcome by planned place of birth. Fortunately, major neonatal and maternal morbidity in women judged to be at “low risk” at term are rare. The incidence of neonatal encephalopathy at term is approximately 1.8 per 1,000 live births (24). However, the incidence of intrapartum stillbirth after labour onset, early neonatal death and other related neonatal morbidity at term is much less certain. A reasonable estimate of the incidence of the composite measure of any neonatal morbidity, the primary outcome for the study, is 3.6 per 1,000 births. As the vast majority of data on neonatal morbidity are from obstetric units, this estimate is assumed to be the incidence of the composite outcome in obstetric units.

In order to have adequate power to detect important clinical differences in outcome that are associated with planned place of birth, the national study will need to collect data on at least 20,000 ‘low risk’ women planning to give birth in an obstetric unit, at least 17,000 women planning to give birth at home and at least 5,000 women planning to give birth in each type of midwifery unit.

Obstetric Units

Since most births in England occur in obstetric units, the national study will collect data from more women planning to deliver in this setting than any of the other settings in order to increase the statistical power of the study. We will aim to collect data on at least 20,000 women planning to give birth in an obstetric unit, who are considered to be at ‘low risk’ of complications at labour onset. As not all women who plan to give birth in an obstetric unit are considered to be ‘low risk’, we will collect data on approximately 30,000 women planning birth in obstetric units, in order to achieve the sample size of at least 20,000 ‘low risk’ women. Data will be collected from a stratified random sample of 28 obstetric units for approximately 3 months in each unit.

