Birth at Home

Although the number of women planning birth at home in England is not known, we do know the number of women who give birth at home, and the most recent published

statistics demonstrate that approximately 15,000 women gave birth at home in England in 2005 (25). Using this and other available data we can estimate the number of women who plan to give birth at home in England. The proportion of women who plan to give birth at home but transfer in labour from home to hospital may be as high as 43% of those who begin a planned home birth and the proportion of women who have unplanned home births may be as high as 50% of those who give birth at home (26, 27). Excluding women who plan birth at home but transfer from home to hospital during labour would underestimate the number of planned home births. Inclusion of unplanned home births would overestimate the number of planned home births. Taking these parameters into account we have estimated the number of women planning birth at home in England to be approximately 15,000 per year. The study aims to collect data on at least 85% of all women planning birth at home over 16 months, that is, from at least 17,000 women.

With data from 17,000 births which were planned to be at home, it will be possible to detect an increase in the incidence of the composite outcome, from 3.6 per 1,000 births in obstetric units to 5.7 per 1,000 for planned home births, at a 5% significance level with 82% power. Alternatively, the study will be able to detect a reduction in the incidence of the composite outcome, from 3.6 per 1,000 births in obstetric units to 2.0 per 1,000 births for home births, at a 5% significance level with 80% power.

Midwifery Units

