Women who transferred from their planned place of birth and had an adverse outcome will be compared to women who transferred and did not have an adverse outcome. Indication for transfer, time from decision to transfer to start of transfer, duration of transfer, and events after the transfer will be investigated as factors that may be associated with adverse outcomes.

In addition, a predefined subgroup analysis will be performed based on outcomes stratified by parity (nulliparous and multiparous). A test for heterogeneity will be performed to investigate whether any differences in outcomes, by planned place of birth, between nulliparous and multiparous women are likely to have been due to chance.

Further exploratory analysis will be performed to generate hypotheses for future research.

Timetable

In December 2007, a decision will be made about whether or not it is feasible to include planned birth at home in the national cohort study. If it is feasible, data collection on planned birth at home will continue on a national level for 16 months, from January 2008 to April 2009. If it is not feasible, the planned birth at home component will not be included in the national study.

Each midwifery unit will collect data for at least 6 months and each obstetric unit will collect data for at least 3 months. However, not all midwifery units or obstetric units will start and finish collecting data at the same time and data in these units will be collected over approximately 7 months, from May to November 2008.

Data analysis will take place over 4 months, from April to July 2009. The results of the study will be disseminated in July and August of 2009.

A detailed timetable is given in Appendix A.

Funding

Birthplace combines the Evaluation of Maternity Units in England (EMU) research programme funded by the NIHR Service Delivery and Organisation (SDO) Programme, and the Birth at Home study, funded by the Department of Health's Policy Research Programme.

Organisation & Governance

Co-investigator Group (CiG)

CiG members will be responsible for assisting the Chief Investigator to achieve governance of the whole programme. The CiG will be accountable to the Department of Health and the NIHR Service Delivery and Organisation (SDO) Programme. Members are drawn from a wide range of maternity care stakeholder groups: clinical, service

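### Over half of the planned home births are collected in months with no obstetric-unit births, so season is partly confounded with setting; a concurrent-period sensitivity analysis should be added

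*Protocol*

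**What the plan says.** The Timetable section sets two collection windows. For home births, if that component proves feasible, "data collection on planned birth at home will continue on a national level for 16 months, from January 2008 to April 2009". For midwifery and obstetric units, "data in these units will be collected over approximately 7 months, from May to November 2008". Within that shorter window "not all midwifery units or obstetric units will start and finish collecting data at the same time", and the sample size section states: "Data will be collected from a stratified random sample of 28 obstetric units for approximately 3 months in each unit".

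The home sample size relies on the whole 16 months. In the sample size section on home birth, "we have estimated the number of women planning birth at home in England to be approximately 15,000 per year", and "The study aims to collect data on at least 85% of all women planning birth at home over 16 months", which gives 17,000 women. On the reference side, "We will aim to collect data on at least 20,000 women planning to give birth in an obstetric unit" who are at low risk. The home comparison is then said to detect a rise "from 3.6 per 1,000 births in obstetric units to 5.7 per 1,000 for planned home births, at a 5% significance level with 82% power", or a fall from 3.6 to 2.0 per 1,000 with 80% power.

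The Analysis section compares each of the other three settings with obstetric units by crude and adjusted odds ratios. The confounders it names are parity, age and deprivation score, followed by an open category of other factors. Season and calendar time are not named, and the difference between the windows is not discussed. Date of delivery is among the core data items for every woman.

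**The concern.** The comparison is not randomised and the outcome is rare, so the home odds ratio is only as good as the comparability of the two groups. The reference group has no births in January to April 2008 or in December 2008 to April 2009. The home group has births in all of those months, and January to April is included twice.

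If the composite outcome, or how completely it is diagnosed and recorded, varies with season, part of that variation will appear as an effect of planning birth at home. The two midwifery-unit comparisons do not have this problem, because those units share the May-to-November window with the obstetric units. At stake is whether the headline safety result for home birth can be read as an effect of setting alone.

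**Working it through.** **1. The plan's own figures.** Home births: 15,000 per year × 16/12 × 0.85 = 17,000, as stated.

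Power is calculated for two proportions by the normal approximation, with pooled variance under the null and a continuity correction:

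power = Φ[(|p1 − p2| − c − 1.96 × SE0) / SE1], where c = (1/n1 + 1/n2)/2.

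The protocol does not state sidedness; two-sided 5% is assumed. With n1 = 20,000 (obstetric) and n2 = 17,000 (home), c = 0.000054.

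- 3.6 versus 5.7 per 1,000: SE0 = 0.000703, SE1 = 0.000716, power 82.4% (stated 82%).
- 3.6 versus 2.0 per 1,000: SE0 = 0.000558, SE1 = 0.000545, power 79.7% (stated 80%).

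Both reproduce. Without the continuity correction they are 84.3% and 82.4%. The stated sample size is not in error.

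**2. Overlap of the windows.** Home: January 2008 to April 2009, 16 months. Obstetric: May to November 2008, 7 months. The non-overlapping home months are January to April 2008 (4) and December 2008 to April 2009 (5), 9 in all. Assuming even monthly accrual:

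- concurrent: 17,000 × 7/16 = 7,438, about 7,440 (43.75%);
- not concurrent: 17,000 × 9/16 = 9,562, about 9,560 (56.25%).

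**3. A steady trend over time.** Measured from 1 January 2008, the home window has its midpoint at 8.0 months and the obstetric window at (4 + 11)/2 = 7.5 months. The gap is half a month, or 1/24 of a year. A linear rise of 10% or 20% per year gives a spurious ratio of about 1 + 0.10/24 = 1.004 or 1 + 0.20/24 = 1.008. With compound growth, averaged month by month, the ratios are 1.005 and 1.010. Either is negligible.

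**4. Season.** Let r be the rate in December to April relative to May to November, with no true effect of setting. The obstetric rate is then the May-to-November rate, and the home-to-obstetric ratio is 7/16 + (9/16) × r.

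| r (assumed) | spurious ratio |
|---|---|
| 0.8 | 0.89 |
| 0.9 | 0.94 |
| 1.1 | 1.06 |
| 1.2 | 1.11 |

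At a rate of 3.6 per 1,000 the odds ratio is practically the same as the rate ratio. For scale, the increase for which the home comparison is sized is 5.7/3.6 = 1.58.

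**5. What a concurrent comparison can show.** With n1 = 20,000 and n2 = 7,438, c = 0.000092:

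- 3.6 versus 5.7: SE0 = 0.000875, SE1 = 0.000970, power 62% (65% without the correction);
- 3.6 versus 2.0: SE0 = 0.000763, SE1 = 0.000669, power 51% (56% without).

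The rates detectable with 80% power move from about 5.6 and 2.0 per 1,000 with all 17,000 home births to about 6.3 and 1.5.

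**The case against.** Several points on the other side are sound.

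- **The long home window has a purpose.** Sixteen months are needed to reach 17,000 home births, whereas 28 obstetric units supply about 30,000 women in about three months each. This explains the mismatch but does not remove it.
- **A reader might infer that any change over time would be attributed to home birth.** The dates do not support that. The home window extends four months before and five months after the obstetric window, so a steady trend almost cancels. Season, or an uneven shift over time, is what remains.
- **A reader might infer that calendar time cannot be adjusted for.** It can, because date of delivery is collected and all settings cover May to November. In a model with month terms, the setting odds ratio is identified essentially from the overlapping months. The cost is precision.
- **A reader might infer that the home odds ratio is known to be biased.** Nothing in the protocol shows seasonal variation in the composite outcome.
- **The confounder list is open, and a detailed analysis plan is to be agreed before data collection starts.** That plan is not shown and may already include month or a concurrent analysis. This stands, and it limits how strongly the point can be put. However, the protocol itself fixes the windows, and no later plan can supply December-to-April obstetric births.
- **The protocol plans no contrast between home and midwifery units.** That the home odds ratio and the midwifery-unit odds ratios rest on different calendar periods is therefore not a fault in any planned analysis.

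**Conclusion.** The point holds as a limited design weakness. About 56% of home births (about 9,560 of 17,000, assuming even accrual) have no concurrent reference births, and December to April contributes to the home group only. Season is partly, not wholly, confounded with setting in the pooled home-versus-obstetric odds ratio. The share would be half or less only if the obstetric window reached eight months, or if home births in the non-overlapping months were captured appreciably less completely than in the others.

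The size and direction of any bias are unknown. The ratios of 1.06 and 1.11 rest on assumed seasonal increases of 10% and 20%; a lower winter rate would bias the other way. Ratios of this order are small beside the 1.58 for which the comparison is sized, but they could matter to an estimate near the null. The midwifery-unit comparisons and the stated sample size are not affected.

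**What to change.** In the Analysis section, add a concurrent-period sensitivity analysis of the primary outcome in low-risk women: home births from May to November 2008 against the obstetric-unit births, adjusted for month of delivery as well as the planned confounders. Report it beside the analysis of all 17,000 home births, and state that the home conclusion is to be read with both. If the detailed analysis plan already contains this, a cross-reference is enough.

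The cost is one extra model on data already collected, with wider intervals. Its power (about 62% and 51%) should be stated in advance, so that a non-significant restricted result is not taken as contradicting the main one.

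Spreading the obstetric windows over all 16 months is not recommended. With midwifery-unit collection unchanged and obstetric births spread evenly, only 20,000 × 7/16 = 8,750 obstetric births would be concurrent with the midwifery units. For 5,000 births in one type of midwifery unit, power in a concurrent comparison would fall from about 80% to about 69% (3.6 versus 6.8 per 1,000) and about 70% (3.6 versus 1.2), by the same continuity-corrected formula. That would move the problem to two comparisons that are now concurrent.

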Appendix A: Timetable

Birthplace: National prospective cohort study

	2007											2008												2009									
	Ma r	Ap r	Ma y	Ju n	Ju l	Au g	Se p	Oc t	No v	De c	Jan	Feb	Mar	Apr	Ma y	Ju n	Ju l	Au g	Se p	Oc t	No v	De c	Ja n	Fe b	Ma r	Ap r	Ma y	Ju n	Ju l	Aug			
Develop protocol																																	
Ethics / R&D approval																																	
Develop and test tools/systems																																	
Contact & engage heads of midwifery																																	
Contact & engage clinical staff																																	
Distribute data collection tools																																	
Feasibility study																																	
Data collection (Birth at Home)																																	
Data collection (MUs & OUs)																																	
Analysis																																	
Advisors meetings																																	
Co-investigator group meetings																																	
Component working group leads meetings																																	
Reporting to SDO/DH																																	
Dissemination																																	

 Note: the hashed boxes indicate that the decision about whether birth at home is considered feasible will be made in December 2007
